### 5.2.2 Visit 3b,c (Day 10 [+4days] post first dose) for MOD-4023 arm only

The following assessments will be conducted at the study site or at the patient's home (if allowed according to local regulations):

- MOD-4023 serum levels.
- Anti-MOD-4023 Abs.
- AEs and local tolerability (aligned with Appendix H) assessment.
- Concomitant medication recording aligned with the questionnaire in [Appendix I](#).

a BA will be done at Visit 2 only in cases where historical bone scans (<6 months prior to Screening) were used to fulfill entry criteria. When performed, BA scans will be completed prior to dosing.

b Applicable only for MOD-4023, Visit 3 assessments, if conducted on Day 14 (dosing day), should be done prior to dosing.

c Blood samples for MOD 4023 treatment group can be collected at site OR at patient's home, based on local regulations and nurse availability. If home visit, a questionnaire, as described in [Appendix I](#), should be completed. If blood sample is collected on Day 14, it should be done prior to dosing.

### 5.2.3 Visit 3 (Day 10 [+4 days] post first dose) for Genotropin arm onlya

- Phone interview and questionnaire completion as provided in [Appendix I](#).
- AEs and local tolerability (aligned with Appendix H) assessment.
- Concomitant medication recording aligned with the questionnaire in [Appendix I](#).

### 5.2.4 Visit 4 (Month 1/Wk 4 [+1wk])

The following assessments will be conducted at Visit 4 on Day 4 (-1) post dose:

- AEs, local tolerability, and concomitant medications.
- Overall health status assessment, including complete physical examination and vital signs.
- Safety laboratory tests: chemistry, hematology and urinalysis.
- Assessment of biochemical markers: IGF-1, IGF-1 SDS, IGFBP-3 and IGFBP-3 SDS serum levels.
- MOD-4023 serum levels (applicable for MOD-4023 arm only).
- Fundoscopy (ONLY if there are signs or symptoms indicative of benign intracranial hypertension).
- Anti-MOD-4023 Abs (MOD-4023 arm only).
- Anti-hGH Abs (Genotropin® arm).
- Return of used and unused injection devices to the site, diary card and PAT forms (USA patients only).
- Drug dispensing and accountability.

### 5.2.5 Visit 5 (Month 3/Wk 13 [ $\pm 1$ wk]), Visit 6 (Month 6/Wk 26 [ $\pm 1$ wk]), Visit 7 (Month 9/Wk 39 [ $\pm 1$ wk]), Visit 8 (Month 12/Wk 52 [ $\pm 1$ wk])

The following assessments will be conducted at Visits 5, 6, 7 and 8 on Day 4 (-1) post dose:

- Auxology measurements: Actual Ht (mean of three consecutive measurements) measured on a calibrated wall mounted stadiometer.
- AEs, local tolerability, and concomitant medications.
- Overall health status assessment, including complete physical examination and vital signs.
- Safety laboratory tests: chemistry, hematology and urinalysis.
- Pubertal status (according to Tanner stages);
- Urine pregnancy test at every visit once a female patient reports first menstrual cycle (menarche).
- Assessment of thyroid function and biochemical markers: TSH, FT4, IGF-1, IGF-1 SDS, IGFBP-3 and IGFBP-3 SDS serum levels.
- Parameters of glucose metabolism: overnight fasting glucose, overnight fasting insulin, HbA1c.
- Parameters of lipid metabolism: overnight fasting cholesterol, triglycerides, HDL, LDL, Lp(a), FFA.

a For the Genotropin® arm a visit by phone interview will be conducted as described in [Appendix I](#).

- Fundoscopy (ONLY if there are signs or symptoms indicative of increased intracranial hypertension).
- BA at Visit 8 only.
- Individual dose adjustment every three months.
- Drug dispensing and accountability.
- MOD-4023 serum levels (MOD 4023 patients only).
- Anti-hGH Ab (Genotropin® patients only).
- ECG (Visit 6 only for Genotropin® patients). Patients in the Genotropin® arm will be requested to inject the study drug preferably at night and come to the clinic the following day for ECG assessment.
- Return of used and unused injection devices and diary cards.
- Return of completed PAT forms (USA only) (Visit 5 only) (applicable for MOD-4023 arm only).
- Anti-MOD-4023 Ab (Visits 5 and 7, MOD-4023 arm only, Visit 8 both arms).
- Informed consent for the LT-OLE (Visit 7 (preferred) or 8).
- QoL questionnaire (QoLISSY) at Visit 8 only.
- For males that are 13 years and older: LH, FSH and testosterone. For females that are 12 years and older: LH, FSH and estradiol (Visit 8 only).

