	
fasting cholesterol, triglycerides, high density lipoprotein (HDL), low density lipoprotein (LDL), lipoprotein a (Lp(a)), Free Fatty Acids (FFA).
 
 
• For males that are 13 years and older: Luteinizing Hormone (LH), Follicle-Stimulating Hormone (FSH) and testosterone. For females that are 12 years and older: LH, FSH and estradiol (Visit 8 only).
 
• Assessment of anti-MOD-4023 Ab (MOD-4023 arm) at Visits 2, 3, 4, 5, 6a, 7, 8a.
 
• Assessment of anti-hGH Ab (Genotropin® arm) at Visits 2, 4, 5, 6, 7 and 8 only.
 
• BA assessments at Visits 1, 2 (at Visit 2 only if historical data was provided for eligibility evaluation and not performed as part of Visit 1) and Visit 8 only.
 
• Fundoscopy (if there are signs or symptoms indicative of benign intracranial hypertension).
 
• ECG at Visit 2 for all patients, pre- dosing and ECG on Visit 6 for patients treated with daily Genotropin®. All MOD-4023 patients will undergo an ECG during Visit 6b, 7-12 hours post dosing.
 
• USA Only - The Participant Assessment Tool (PAT) completed at Wks 1, 2, 3, 4, 5 and 6 for MOD-4023 treated patients. In any given wk a new PAT will be completed for each PEN used that wk (in some cases more than 1 PEN may be used for full dose administration, in which case a PAT will be completed for each PEN used that wk. In some cases, more than 1 injection from the same PEN may be needed, in which case only 1 PAT is completed for that PEN that wk).
 
• USA Only - The Observer Assessment Tool (OAT) completed at Wk 1 for MOD-4023 treated patients. A new OAT will be completed for each PEN used (in some cases more than 1 PEN may be used for full dose administration, in which case an OAT will be completed for each PEN used. In some cases, more than 1 injection from the same PEN may be needed, in which case only 1 OAT is completed for that PEN). Wk 1 corresponds to study Visit 2, which will be at the site.
 
• Individual dose adjustment every three months based on weight.
 
• Drug dispensing Visits 2, 4, 5, 6, 7 and 8 (for patients entering the LT-OLE).
 
• QoL questionnaire (Visits 2 and 8 only); patients below the age of 7 and 0 days will be completing the questionnaire with their parents/legal guardians using a parent questionnaire while patients above and including the age of 7 and 0 days will be encouraged to use the child questionnaire. The QoL questionnaire will be completed in specific countries (determined by availability of validated translated tools) as described in Appendix L.
 
 
For MOD-4023 patients arm only, Visit 3 (Day 10 [+4 days] post first dose), Visits 6a (Month 6/Wk 26 [<math>\pm</math>3 wks]) and Visit 8a (Month 12/Wk 52 [<math>\pm</math>1 wk]) will be conducted on dosing day, blood samples will be taken pre-dose for assessment of MOD-4023 serum levels. These blood samples can be collected at site OR at patient's home, based on local regulations and nurse availability. If home visit, a questionnaire as described in Appendix I should be completed.
 
For Genotropin® patients on Day 10 (+4 day) post first dose a phone interview will be conducted according to the questions as provided in Appendix I.

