### 5.2.1 Visit 2 (Day 1/Baseline) – recommended injection days as indicated in [Appendix E](#)

Visit 2 must be conducted within 2 wks of randomization.

The following assessments will be conducted on Day 1/Baseline:

a 1. Western Europe, Israel, Australia, New Zealand, Canada and USA; 2. Central and Eastern Europe, Greece, Turkey, Latin America and Asia except for India and Vietnam 3. India and Vietnam.

b All visits, except Visit 3, can be conducted within the specified window to accommodate patient availability, but must be conducted on day 4 (-1) post dose.

c Applicable only for MOD-4023, Visit 3 assessments, if conducted on Day 14 (dosing day), should be done prior to dosing.

Effective Date: Date of final electronic approval

- Auxology measurements: Actual Ht (mean of three consecutive measurements) measured on a calibrated wall mounted stadiometer.
- AEs, local tolerability (aligned with Appendix H), and concomitant medications.
- Overall health status assessment, including complete physical examination and vital signs.
- Safety laboratory tests: chemistry, hematology and urinalysis.
- Pubertal status (according to Tanner stages).
- Assessment of thyroid function and biochemical markers: TSH, FT4, IGF-1, IGF-1 SDS, IGFBP-3 and IGFBP-3 SDS serum levels.
- Assessment of MOD-4023 serum levels (applicable for MOD-4023 arm only).
- Parameters of glucose metabolism: overnight fasting glucose, overnight fasting insulin, HbA1c.
- Parameters of lipid metabolism: overnight fasting cholesterol, triglycerides, HDL, LDL, Lp(a), FFA.
- Assessment of anti-MOD 4023 and anti-hGH Ab (depending on arm of study).
- BAa.
- ECG pre-dosing.
- Training for patients, parents or legal guardians on drug administration.
- Fundoscopy (if there are signs or symptoms indicative of benign intracranial hypertension).
- Training for patients, parents or caregiver for completing the PAT assessment.
- Administration of study drug at the study site by patient or parent/caregiver.
- MOD-4023 on-site OAT assessment (USA only).
- MOD-4023 on-site PAT assessment (USA only).
- QoL Questionnaire completion (in specific countries as indicated in [Appendix L](#)).
- Drug dispensing and accountability.

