Patients who are off treatment for more than 90 days due to technical reasons e.g. delay in approval of Protocol Amendment may be allowed to continue into the LT-OLE after confirmation of availability of all required baseline LT-OLE assessments (Visit 8/10). The following tests and assessments must be repeated:

- Safety laboratory tests: chemistry, hematology and urinalysis.
- Parameters of glucose metabolism: overnight fasting glucose, overnight fasting insulin, HbA1c.
- Assessment of anti-MOD-4023 Ab for all patients (Genotropin® group – baseline for future tests).
- Assessment of biochemical markers: IGF-1, IGF-1 SDS, IGF-BP-3 and IGF binding protein-3 (IGFBP-3) SDS serum levels.

5.3.1 Visit 11 (Month 12, Day 10 [+4days] post first MOD-4023 dose) for patients switching from Genotropin® to MOD-4023 only

The following assessments will be conducted at the study site or at the patient's home (if allowed according to local regulations):

- MOD-4023 serum levels.
- Anti-MOD-4023 Abs.
- AEs and local tolerability (aligned with Appendix H) assessment.
- Concomitant medication recording aligned with the questionnaire in [Appendix I](#).

5.3.2 Visit 12 (one month post first MOD-4023 dose(Month 13 [ $\pm 2$ wk])) will be performed on site for patients switching from Genotropin® to MOD-4023

The following assessments will be conducted at Visit 12 on Day 4 (-1) post dose:

- AEs, local tolerability, and concomitant medications.
- Overall health status assessment, including complete physical examination and vital signs.
- Urine pregnancy test once a female patient reports first menstrual cycle (menarche).
- Safety laboratory tests: chemistry, hematology and urinalysis.
- Assessment of biochemical markers: IGF-1, IGF-1 SDS, IGFBP-3 and IGFBP-3 SDS serum levels.
- Fundoscopy (ONLY if there are signs or symptoms indicative of benign intracranial hypertension).
- MOD-4023 serum levels.
- Anti-MOD-4023 Abs.
- Fundoscopy (ONLY if there are signs or symptoms indicative of benign intracranial hypertension).
- Return of used and unused injection devices to the site and diary card.
- Drug dispensing and accountability.

Existing MOD-4023 patients will have a telephone visit at Visit 12 (one month post LT-OLE entry [Month 13  $\pm 2$ wk]) to ask about AEs, local tolerability and concomitant medications. This visit will be completed using the questionnaire in Appendix I.

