### 5.8.9 Laboratory Assessments

All routine clinical laboratory assessments will be performed by central laboratory as provided in [Appendix K](#) according to the schedule in [Appendix A](#), other than urine pregnancy testing, when required, which will be conducted at the local laboratory. The laboratory evaluations will include:

1. Hematology: Red Blood Cell (RBC) count, hemoglobin (HGB), hematocrit (HCT), Mean Cell Hemoglobin (MCH), Mean Cell Hemoglobin Concentration (MCHC), Mean Corpuscular Volume (MCV), White Blood Cell (WBC) count and differential, platelet count, prothrombin time (PT)/international normalized ratio (INR), partial thromboplastin time (PTT) (if indicated only).
2. Serum chemistry: total protein, albumin, total bilirubin, alanine aminotransaminase (ALT), aspartate transaminase (AST), gamma-glutamyl transferase (GGT), lactate dehydrogenase (LDH), creatinine phosphokinase (CPK), alkaline phosphatase, sodium, potassium, calcium, phosphate, blood urea nitrogen (BUN), liver function test (LFT), creatinine.
3. Lipid metabolism: overnight fasting cholesterol, triglycerides, high density lipoprotein (HDL), low density lipoprotein (LDL), lipoprotein a (Lp(a)), Free Fatty Acids (FFA).
4. Glucose metabolism: overnight fasting glucose and insulin, HbA1C.
5. Thyroid function: TSH, FT4.
6. Immunogenicity: anti-MOD-4023 Ab (MOD-4023 arm only during the main study and all patients during the LT-OLE) and Abs to r-hGH (all patients). It is recommended that if the Genotropin patients normally administer their drug in the morning, that they wait on those visit days to administer the Genotropin® until after the blood sampling.
7. IGF-1, IGF-1 SDS, IGFBP-3 and IGFBP-3 SDS levels.
8. MOD-4023 serum levels (MOD-4023 arm only during the main study and all patients during the LT-OLE).
9. Urinalysis: pH, glucose, ketones, erythrocytes, leukocytes, protein.
10. Urine pregnancy test.
11. Luteinizing hormone (LH), Follicle-stimulating hormone (FSH) and testosterone (for males that are 13 years and older).
12. LH, FSH and estradiol (for females that are 12 years and older).

For further details on blood sample collection and shipment to the central laboratory, please refer to the Central Laboratory Manual.

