## APPENDIX A: STUDY FLOW CHART / SCHEDULE OF EVENTS

### Main Study

Study Procedure	Screening		Baseline	Treatment								Follow-up b	
Study Day ( $\pm$ in dy/s)	a -56 to -1		1/	10 (+4)							EOS b		
Study Wk ( $\pm$ in wk/s)	-8 to -1 (+4) a		0 (+4 from Eligibility)		4 (+1)	13 ( $\pm$ 1)	26 ( $\pm$ 1)	26 ( $\pm$ 3)	26 ( $\pm$ 3)	39 ( $\pm$ 1)	52 ( $\pm$ 1)	52 ( $\pm$ 1)	56 ( $\pm$ 5 days)
Study Month	-2		0	0.5	1	3	6	6	6	9	12	12	13
Study Visit	1		2	3	4	5	6	6a c	6b	7	8/10 d	8a c /10 d	9
Informed consent	X									X e	X f		
Inclusion/exclusion criteria	X										X e		
Demographic & medical history including parent Ht	X												
Auxology measurements g	X		X			X	X			X	X		
Physical examination and vital signs h	X		X		X	X	X			X	X		
ECG			X pre-dose				X i		X j				
Pubertal status (Tanner stages)	X		X			X	X			X	X		

a For the screening period, additional 4 wks might be added due to technicalities or patient's benign illness.

b If ET during the main study or **not** continuing to LT-OLE.

c Dosing day (assessments will be conducted pre-dose). This visit is applicable only for patients in MOD-4023 arm.

d Visit 8 if EOS at completion of the main study, Visit 10 if continuing to LT-OLE.

e If continuing to LT-OLE.

f Informed consent for the LT-OLE may be obtained at Visit 7 or Visit 8.

g Actual Ht (mean of 3 consecutive measurements per patient per visit) measured on a calibrated wall mounted stadiometer.

h Body weight, ideally fasted in the morning, without shoes and having removed all outwear and heavy pocket items.

i Genotropin® patients.

j ECG will be conducted at 7-12 hours post-dose (MOD-4023 arm only). Patients will be requested to inject MOD-4023 during the day/night at their convenience and come to the clinic at the requested time point for ECG.

Effective Date: Date of final electronic approval

Study Procedure	Screening		Baseline	Treatment								Follow-up b	
Study Day ( $\pm$ in dy/s)	a -56 to -1		1/	10 (+4)							EOS b		
Study Wk ( $\pm$ in wk/s)	-8 to -1 (+4) a		0 (+4 from Eligibility)		4 (+1)	13 ( $\pm$ 1)	26 ( $\pm$ 1)	26 ( $\pm$ 3)	26 ( $\pm$ 3)	39 ( $\pm$ 1)	52 ( $\pm$ 1)	52 ( $\pm$ 1)	56 ( $\pm$ 5 days)

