SHOX gene evaluation aa	X												
IGF-1, IGF-1 SDS, IGFBP-3, and IGFBP-3 SDS	X		X		X	X	X			X	X		
MOD-4023 serum levels bb			X	X	X	X		X		X		X	
Thyroid function (TSH, fT4)	X		X			X	X			X	X		
Glucose metabolism cc	X		X			X	X			X	X		
Lipid profile dd			X			X	X			X	X		
LH, FSH and testosterone ee											X		
LH, FSH and estradiol ff											X		

x Urinalysis: pH, glucose, ketones, erythrocytes, leukocytes, protein.

y Two (2) different GH stimulation (provocation) tests (ITT, with serum cortisol response to hypoglycemia if insulin stimulation test is chosen OR arginine test/clonidine test/glucagon test (with or without propranolol)/L-dopa plus propranolol.

z ACTH or CRH stimulation test will be conducted if morning cortisol is below 190 nmol/L (7 µg/dL), and only if the patient was not previously assessed for the hypothalamus-pituitary-adrenal axis. ITT with serum cortisol response to hypoglycemia is adequate for assessment of adrenal insufficiency and no ACTH stimulation test is required if such results are available. Historical ACTH test is acceptable

aa Historical data is acceptable.

bb For MOD-4023 arm only.

cc Glucose metabolism: fasting glucose and fasting insulin; HbA1c.

dd Lipid profile: overnight fasting total cholesterol, LDL cholesterol and triglycerides, HDL and FFA; Lp(a) once every 3 months.

ee For male patients that are at the age of 13 years and above.

Effective Date: Date of final electronic approval

Study Procedure	Screening		Baseline	Treatment								Follow-up b	
Study Day ( $\pm$ in dy/s)	a -56 to -1		1/	10 (+4)							EOS b		
Study Wk ( $\pm$ in wk/s)	-8 to -1 (+4) a		0 (+4 from Eligibility)		4 (+1)	13 ( $\pm$ 1)	26 ( $\pm$ 1)	26 ( $\pm$ 3)	26 ( $\pm$ 3)	39 ( $\pm$ 1)	52 ( $\pm$ 1)	52 ( $\pm$ 1)	56 ( $\pm$ 5 days)
Study Month	-2		0	0.5	1	3	6	6	6	9	12	12	13
Study Visit	1		2	3	4	5	6	6a c	6b	7	8/10 d	8a c /10 d	9
Abs to r-hGH (Genotropin arm)			X		X	X	X			X	X		
Abs to r-hGH (all patients)	X												
Abs to MOD-4023			X	X	X	X		X		X		X	

ff For female patients that are at the age of 12 years and above.

Effective Date: Date of final electronic approval

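### The protocol conflicts on whether Genotropin patients give an anti-MOD-4023 sample at Visit 8/10, so switchers may lack a pre-exposure sample and SAP 3.5.4 would then class them antibody negative by default

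*Protocol*

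**What the plan says.** Under protocol Section 5.3, Genotropin patients who continue start MOD-4023 at Visit 8/10. The next anti-MOD-4023 sample listed for them is Visit 11, Day 10 (+4) after that dose. Antibody formation against MOD-4023 is an LT-OLE safety endpoint (Section 8.4.6).

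Four places set the month-12 sample:

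- Section 5.2.5: "Anti-MOD-4023 Ab (Visits 5 and 7, MOD-4023 arm only, Visit 8 both arms".
- Synopsis, Study Procedures: "Assessment of anti-MOD-4023 Ab (MOD-4023 arm) at Visits 2, 3, 4, 5, 6a, 7, 8a". For the other arm it gives "Assessment of anti-hGH Ab (Genotropin® arm) at Visits 2, 4, 5, 6, 7 and 8 only".
- Section 5.8.9: "anti-MOD-4023 Ab (MOD-4023 arm only during the main study and all patients during the LT-OLE".
- Appendix A, Main Study: the row "Abs to MOD-4023" is marked at Visits 2, 3, 4, 5, 6a, 7 and in the column headed 8a/10. The 8/10 column is empty. Footnote c, attached to 6a and 8a, says "This visit is applicable only for patients in MOD-4023 arm", and Section 5.2.6 agrees.

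At Visit 2, Section 5.2.1 has "Assessment of anti-MOD 4023 and anti-hGH Ab (depending on arm of study".

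For treatment gaps after Visit 8, the synopsis and Section 5.3 draw a line at 90 days. Below it, only training, dosing and a local tolerability check are needed. Above it, several tests have to be repeated. One is anti-MOD-4023 antibody in all patients, described for the Genotropin group as the "baseline for future tests".

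SAP 3.5.4 calls a patient ADA positive in two situations: a positive test after drug when the main-period baseline was negative, or a titer more than four times a positive main-period baseline. Everything else is ADA negative.

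**The concern.** Antibody newly formed on MOD-4023 can be told from reactivity that was already there only with a sample taken before the first MOD-4023 dose. For a switcher that moment is Visit 8/10. If the sample is missed, it cannot be recovered.

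The passages a site is most likely to work from, the synopsis and Appendix A, do not clearly ask for it. Sites may therefore collect it inconsistently.

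What is at stake is the antibody result in about half of the extension population. SAP 6.2.1 tabulates anti-somatrogon antibody by year and visit. SAP 6.1.1 allows efficacy summaries by ADA status and titer, so a wrong status can also carry into those tables.

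**Working it through.** The plan states no figure on this point, so there is none to reproduce. The check compares the schedules, applies the SAP rule and counts the children who could be affected.

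**1. Month-12 anti-MOD-4023 sample in the Genotropin arm**

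| Place | Sample? |
|---|---|
| Section 5.2.5 | Yes, Visit 8 |
| Synopsis | No; anti-hGH only |
| Section 5.8.9 | No in the main study; yes once in the LT-OLE |
| Appendix A | 8/10 blank; 8a/10 marked, with 8a limited to the MOD-4023 arm |

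One place asks for it plainly. The synopsis does not, and the other two depend on whether the visit is read as 8, 8a or 10.

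**2. Other possible sources of a pre-exposure sample**

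- Visit 2: the assay depends on arm, and the synopsis gives the Genotropin arm anti-hGH only. A main-period anti-MOD-4023 baseline is therefore not clearly collected in that arm.
- Extra steps for switchers at Visit 8/10 (synopsis and Section 5.3): dispensing, training and administration, local tolerability. No antibody sample is listed.
- Gap under 90 days: no sample required.
- Gap over 90 days: sample required. Patients who start at Visit 8/10 fall outside this provision.

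**3. SAP 3.5.4 applied to each case**

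Let b be the main-period baseline titer and p the post-dose titer, on the SAP's scale of 0, 10, 50, 250, 1250, 6250. The rule is: positive if b = 0 and p > 0; positive if b > 0 and p > 4b; otherwise negative.

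| b | Positive when |
|---|---|
| 0 | p is 10 or more |
| 10 | p > 40, so 50 or more |
| 50 | p > 200, so 250 or more |
| missing | never: negative at all 6 titers, including 6250 |

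With b missing, neither positive condition can be met and the closing default applies. Collecting the Visit 8/10 sample alone changes nothing here, because the rule refers to the main-period baseline.

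**4. Number of children**

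Section 8.1 randomizes 110 to Genotropin and allows about 10% dropout: 110 x (1 - 0.10) = 99 potential switchers. With the same dropout in the other arm, that is about half of those entering the LT-OLE.

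**The case against.** The strongest reply is that the sample is intended and the text can be read that way.

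- Tests to be repeated after a long gap were presumably due at Visit 8/10 in the first place. The rule for shorter gaps then only means that no repeat is needed.
- The Appendix A antibody row has no arm label, while neighboring rows do. Its column is headed 8a/10, and footnote d makes that Visit 10 for anyone continuing. Some marks in the column carry a footnote that provides for the Genotropin arm.
- Section 5.8.9 covers all patients once the LT-OLE begins, and Visit 10 is its first visit.

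This stands as evidence of intent, and it means that Appendix A is ambiguous rather than a clear exclusion. It does not settle what a site will do: the synopsis line names one arm, footnote c names one arm, and the list of steps for switchers has no antibody sample.

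A second reply is that the Genotropin arm is tested for anti-hGH at Visit 8, so reactivity raised on Genotropin would be seen. That stands in part. MOD-4023 also carries three CTP copies (Section 1.3), and an anti-hGH result supplies no anti-MOD-4023 titer for the fourfold comparison.

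A third is that the LT-OLE is descriptive, with no hypothesis tests. That is correct and limits the consequence to tabulated incidence and the ADA subgroup summaries.

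**Conclusion.** The passages conflict and need to be reconciled. Up to about 99 switchers could start MOD-4023 without a pre-exposure sample. That count assumes the planned 10% dropout, that all completers continue, that none has a gap over 90 days, and that every site follows the synopsis or the narrow reading of Appendix A. Sites that follow Section 5.2.5 will have the sample.

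The direction of the error depends on how the SAP is applied. Read literally, it classes a switcher with no main-period anti-MOD-4023 baseline as negative, so incidence is understated. If analysts treat the missing baseline as negative, any reactivity present before the switch is counted as new.

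A reader might infer that these children cannot be scored at all. The SAP does score them, through its default. A reader might also infer that incidence among switchers would be inflated by a calculable amount. The documents give no prevalence of pre-existing reactivity, and inflation arises only under the second reading, so no such figure can be supported.

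The primary 12-month comparison is not affected.

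**What to change.** In the protocol, reconcile six places: the synopsis antibody line, the synopsis list of steps for switchers, Section 5.2.5, the Section 5.3 list of steps for switchers, Section 5.8.9 and the Appendix A antibody row. Each should say that Genotropin patients continuing to the LT-OLE give an anti-MOD-4023 sample at Visit 8/10, before the first MOD-4023 dose. The MOD-4023 arm's month-12 sample should stay at pre-dose Visit 8a. Simply writing both arms at Visit 8 into the synopsis would add a Day 4 (-1) sample in that arm beside the 8a one.

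In SAP 3.5.4, define the ADA baseline for switchers as the last sample before the first MOD-4023 dose. This also picks up the repeat sample after a long gap. State how a switcher with no such sample is reported, so that the default does not decide it.

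Both changes are needed: the sample alters no classification until the SAP uses it, and the SAP rule needs a sample to refer to. The cost is wording in about six protocol places and one SAP rule, plus one assay per switcher on blood drawn at an existing visit.
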